### 9.2 Primary Endpoint(s)

The Hyperphagia in Prader-Willi Syndrome questionnaire (HPWSQ-R) is an informant-based tool for examining the psychological, developmental, and neurobiological correlates of hyperphagia in PWS. The items measure hyperphagic symptoms are reported by caregivers and are rated on a five-point scale (1: not at all/none of the time/extremely easy to 5: extremely/all of the time/extremely hard). HPWSQ-R Questionnaire is classified into 3 domains; behavior, drive, and severity.

Subdomain	Question
Hyperphagic Behavior	1d. How “clever” or “fast” was your child in obtaining food? 2a. Try to bargain or manipulate to get more food 2b. Forage through the trash for food

	2c. Get up at night to food seek 2e. Try to steal food
Hyperphagic Drive	1a. How upset did your child generally become when denied a desired food? 1b. How persistent was your child in asking or looking for food after being told “no” or “no more”? 1c. How distressed did your child become when stopped from talking about food or engaging in food-related behaviors? 3. Once food on mind, how easy to redirect away from food
Hyperphagic Severity	1e. To what extent did food-related thoughts, talk, or behaviour interfere with your child’s normal daily routines, self-care, school, or work 2d. Talk about food or engaged in food-related behaviors, outside of normal meal times

The subscore for a domain is defined as the sum of all item scores in the domain. Total score is the sum of these three subscores. Total score will be missing if any subscore is missing. Missing item scores and total score will be handled as described in the section 9.1.

### **9.2.1 Primary Variable(s) Analysis**

The primary variable is change in HPWSQ-R total score from baseline to Visit 4 (Day 15) and will be analyzed in the FAS population using an analysis of covariance (ANCOVA) model with treatment and site as fixed effects and HPWSQ-R total score at baseline as a covariate. The treatment group difference in total score between placebo and carbetocin will be calculated by subtracting the mean change from baseline in placebo from that in the carbetocin group. A borderline statistically significant difference at the 10% significant level will be achieved if the upper limit of the 90% 1-sided confidence interval (CI) for the treatment difference is less than zero. The corresponding p-value will be reported as well.

Summary of HPWSQ-R total score will be presented as well as a box-and-whisker plot of change in HPWSQ-R total score by visit.

### **9.2.2 Sensitivity Analyses**

The analysis of the primary endpoint in the section 9.2.1 will be also conducted based on the subjects in the PP population and ITT population.

In addition, the primary endpoint will be analyzed using repeated measures analysis with treatment, site, visit and treatment-by-visit interaction as fixed effects and HPWSQ-R total score at baseline as a covariate. An unstructured working correlation matrix will be used for the analysis. LOCF will not be used to impute missing values because it would affect the correlation of observations between weeks. The two treatment groups will be compared at Visit 4 (Day 15). The LS means, the LS mean difference, and 90% 1-sided confidence interval (CI) for the treatment difference will be presented will be presented at each visit as well.

### 9.3 Secondary Endpoint(s)

Secondary endpoints include Clinical Global Impression-Improvement after treatment (CGI-I) score at Day 8 and Visit 4, change from Visit 2/Baseline to Day 8 and Visit 4 for the following measurements:

- HPWSQ-R hyperphagia behavior, drive, and severity domain scores
- HPWSQ-R-C total score
- HPWSQ-R-C hyperphagia behavior, drive, and severity domain scores

and change from Visit 1/Baseline to Day 8 and Visit 4 for the following measurements:

- CY-BOCS total score
- Food Domain of the Reiss Profile

The improvement of PWS symptoms will be assessed by the Clinical Global Impression (CGI). The CGI scale is a 7-point clinician rating of illness severity (1 = no illness, 7 = extremely ill), at the beginning of the trial and a 7-point clinician rating of improvement of patient condition (1 = very much improved, 7 = very much worse), during and at the end of the trial.

HPWSQ-R-C scale consists of the same 11 questions and has the same scoring as HPWSQ-R. HPWSQ-R-C is administered by the same clinician throughout the trial while the HPWSQ-R scale is administered by the parent or caregiver.

The CY-BOCS is a clinician rated, semi-structured inventory of specific symptoms and symptom severity (0 = none, 4 = extreme) in pediatric obsessive-compulsive disorder (OCD). It includes 2 primary components: the Symptom Checklists and Severity Scale. The 10 severity items are summed to produce an Obsessions Severity Score (5 items), Compulsions Severity Score (5 items), and Total score (sum of all 10 severity items).

The food domain of the Reiss Profile consists of 7 questions that pertain to food seeking behaviour. For analysis purpose, the scales of Food Domain of the Reiss Profile will be scores as follows:

Scales of Food Domain of the Reiss Profile	Score
Strongly Disagree	-2
Disagree	-1
Neutral	0
Agree	1
Strongly Agree	2

Total score of Food Domain of the Reiss Profile is defined as the sum of all individual item scores.

The secondary endpoints will be analyzed in a similar fashion as the primary endpoint. All analysis of secondary endpoints will be conducted using ANCOVA model treatment and site as fixed effects

and baseline score as a covariate. Clinical Global Impression - Severity (CGI-S) will be used as baseline covariate for CGI-I analysis.

#### **9.4 Exploratory Analyses**

The relation between the primary endpoint and the secondary endpoints will be explored by visit for the FAS population using the Pearson correlation coefficients. An ad-hoc analysis might be performed to further explore the relation between the primary endpoint and the secondary endpoints.

## 10 Safety

### 10.1 General Considerations

Safety parameters will be evaluated for the safety analysis set. Complete listings and summary tables for all safety information, including adverse events, clinical laboratory safety data, physical examination, nasal examination, vital signs, and ECG will be presented. No formal statistical analysis will be performed.

Unscheduled assessments prior to the first IMP administration will be included to derive baseline while post-baseline unscheduled assessments will not be included in the data analysis unless specified.

### 10.2 Adverse Events

Adverse events (AEs) are classified according to the MedDRA version 16.1 give a system organ class and preferred term for each event.

A treatment-emergent adverse event (TEAE) is any adverse event that begins during the treatment period or worsening of a pre-existing medical condition. The Treatment Period is the period during which a subject receives IMP (including the residual time of drug effect). More specifically, for subjects who completing all doses as planned on Day 14, the Treatment Period is Day 1 to Day 15. For subjects who discontinued IMP, the Treatment Period is Day 1 to the dose date + 1.

TEAEs will be listed by treatment and subject, and the incidence of TEAEs will be presented by treatment. In addition, TEAEs will be presented by causality (relationship to the trial medication) and intensity (severity) and seriousness. Serious adverse events (SAEs) and adverse events leading to discontinuation will be listed.

If a subject has an AE with unknown intensity, then the subject is counted in the category of “Severe”. If an AE with unknown relationship to IMP, then the AE is considered to be related to IMP.

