**Table 1 Schedule of Activities**

Period:	Screening	Treatment					End of Treatment Visit / Early termination visit	F/U phone call
		Baseline			1-Week Assessment			
Visit:	1	2	3				4	
Days:	-7 to 0	1	2	3-7	8 (+/-1)	9-14	15	19 (+/-3)
IMP Dosing:	NA	On site	On site	Off site			On site	NA
Assessments								
Written informed consent and assent	X							
Inclusion/exclusion criteria	X							
Prior/concomitant medication	X	X	X		X		X	
Physical examination	X						X	
Nasal examination a	X	X	X				X	
Medical history	X							
Demographics	X							
Urine drug and alcohol screen	X						X	
Urine pregnancy test	X						X	
Height and Weight	X						X	
Vital signs b	X	X	X				X	
Electrocardiogram c	X	X	X				X	
Blood samples for clinical chemistry, hematology, hemostasis, and urinalysis	X		X				X	
Blood samples for pharmacokinetics d		X	X					
Nutritional phase assessment	X							
Randomization e		X e						
HPWSQ-R and HPWSQ-R-C	X	X			X		X	
CGI-S		X						
CGI-I					X		X	
CY-BOCS	X				X		X	
Food Domain of Reiss Profile	X				X		X	
IMP administration training		X						
Dispense IMP		X	X	X	X	X		
Return IMP							X	
IMP dosing		X	X	X	X	X		
Adverse events	X	X	X		X		X	X

CGI-I=Clinical Global Impression-Improvement after treatment; CGI-S=Clinical Global Impression-Severity; CY-BOCS= Children's Yale-Brown Obsessive-Compulsive scale; F/U=follow-up; HPWSQ-R=Hyperphagia in Prader-Willi Syndrome Questionnaire-Responsiveness; HPWSQ-R-C=Hyperphagia in Prader-Willi Syndrome Questionnaire-Clinician ; IMP=investigational medicinal product

- a Nasal examinations to be done at Visit 1 (anytime), within 1 hour prior to each dose at Visit 2 and Visit 3, and at Visit 4 (anytime).
- b Includes pulse, respiration rate, blood pressure and body temperature. At Visit 2 and 3, vital signs will be monitored prior to and after IMP dosing at 30-minute intervals for 2 hours after each dose.
- c ECG to be done within 1 hour after morning dose at Visit 2 and 3.
- d Three blood samples to be collected at Visit 2 and Visit 3, according to the schedule specified in section 7.2.6 Clinical Laboratory Tests/Pharmacokinetic Assessments. All PK labs are to be done prior to subsequent dose.
- e Randomization will be done within 24 hours prior to the Visit 2, morning dose.

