### **7.2.3 Nasal Examination**

Nasal examinations will be done at Visit 1, within 1 hour prior to each dose at Visit 2 and Visit 3, and at Visit 4 (anytime).

Grading will be conducted according to the following scale:

Grade 0 = no abnormal findings

Grade 1A = focal nasal mucosal inflammation, erythema, or hyperemia

Grade 1B = superficial nasal mucosal erosion

Grade 2 = moderate nasal mucosal erosion

Grade 3\* = nasal mucosal ulceration

Grade 4\* = nasal septum perforation

\*Note: After randomization, grading of 3 or 4 will be documented as an adverse event. If deemed appropriate, additional follow-up examinations will be performed at the discretion of the Investigator.

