## **8 ADVERSE EVENTS**

### **8.1 Adverse Event Definition**

An adverse event is any untoward medical occurrence in a subject participating in a clinical trial. It includes:

- Any unfavorable and unintended sign, symptom or disease temporally associated with the use of the IMP, whether or not considered to be caused by the IMP.
- Adverse events commonly observed and adverse events anticipated based on the pharmacological effect of the IMP.
- Any laboratory abnormality, vital sign or finding from physical (or gynecological) examination assessed as clinically significant by the investigator (note: findings from assessments and examinations done during screening are not adverse events, but are recorded as medical history).
- Accidental injuries, reasons for any change in medication (drug and/or dose), reasons for any medical, nursing or pharmacy consultation, or reasons for admission to hospital or surgical procedures.
- Overdoses and medication errors with and without clinical consequences.

An adverse drug reaction is an adverse event evaluated by the investigator as being probably or possibly causally related to treatment with the IMP.

A serious adverse drug reaction is a serious adverse event (SAE) evaluated by the investigator and/or by Ferring as having a reasonable possibility of causal association with IMP.

An unexpected adverse event is an adverse event not identified in nature, severity, or frequency in the section “Undesirable Effects” in the sponsor’s current Investigator’s Brochure.

A treatment-emergent adverse event is any adverse event that begins during the Treatment Period or worsening of a pre-existing medical condition. The Treatment Period is the period during which a subject receives IMP.

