### **Date and Time of Onset**

The date of onset is the date when the first sign(s) or symptom(s) were first noted. If the adverse event is an abnormal clinically significant laboratory test or outcome of an examination, the onset date is the date the sample was taken or the examination was performed.

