##### **10.5.1 Nasal examination**

Baseline for nasal examination analyses will be the values obtained at the last assessment prior to the first dose of IMP. End of trial will include the last post-baseline observation during the trial.

Number (%) of subjects with each grade of nasal examination result will be summarized by treatment, visit and timepoint. In addition, the changes in nasal examination result by treatment, visit and timepoint are presented with shift tables with total number of subjects, and number and percent of subjects who experienced a shift.

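### SAP 10.2 starts the treatment-emergent window at calendar Day 1, so an adverse event with onset that day but before the first dose is counted as a TEAE

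*Combined protocol and SAP*

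**What the plan says.** Protocol 8.1 calls an adverse event treatment-emergent if it begins in the Treatment Period or is a worsening of a pre-existing condition, and adds: "The Treatment Period is the period during which a subject receives IMP". SAP 10.2 opens the same way, "The Treatment Period is the period during which a subject receives IMP (including the residual time of drug effect", and then makes the window specific. For completers, "for subjects who completing all doses as planned on Day 14, the Treatment Period is Day 1 to Day 15". For the others, "For subjects who discontinued IMP, the Treatment Period is Day 1 to the dose date + 1". Both rules begin at Day 1 as a date.

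Elsewhere the dividing line is the first administration:

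- Footnote a to Protocol 8.2.2 labels an adverse event with onset before the first IMP administration as pre-treatment.
- SAP 7.3 separates prior from concomitant medication at first IMP administration.
- SAP 10.4.1 does the same for the vital-sign baseline, and SAP 10.5.1 for the nasal one: "Baseline for nasal examination analyses will be the values obtained at the last assessment prior to the first dose of IMP".

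Day 1 is Visit 2. Protocol 6.1.2 places a nasal examination in the hour before each dose, vital signs before dosing, and adverse event collection on that day. Under Protocol 8.2.1, collection has been running since consent.

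**The concern.** SAP 10.2 contains two starts for one window: the moment IMP is first received, and the start of the calendar day on which that happens. They differ by the hours before the morning dose on Day 1. A programmer is likely to code the specific rule, which is the calendar one. An event that preceded any exposure would then appear in the TEAE tables.

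Safety is reported descriptively, without formal testing (SAP 10.1), so these tables carry the tolerability message. An event that began before the first dose cannot be a drug effect and only adds noise to a comparison of about 19 subjects per arm.

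**Working it through.** No power or sample-size figure depends on this point. The check sets the rules side by side.

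1. **The interval.** The morning dose is given between 06:00 and 09:00 (Protocol 3.1.1). The disputed interval therefore runs from 00:00 on Day 1 to a time between 06:00 and 09:00. It contains the scheduled pre-dose nasal examination and vital signs.

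2. **What can become an adverse event in it.** Three routes remain open:
   - a new symptom that morning;
   - a new pre-dose finding that the investigator judges clinically significant (Protocol 8.1);
   - a nasal grade 3 or 4, because Protocol 7.2.3 sets the trigger at randomization and not at dosing: "After randomization, grading of 3 or 4 will be documented as an adverse event". Table 1, footnote e, says "Randomization will be done within 24 hours prior to the Visit 2, morning dose", so the pre-dose examination can follow randomization, although the order is not fixed.

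   Two groups are excluded. Screening findings go to medical history (Protocol 8.1). Pre-existing conditions become adverse events only if they worsen after IMP (Protocol 8.2.2).

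3. **Its date.** For an adverse event that is an examination finding, "the onset date is the date the sample was taken or the examination was performed". A pre-dose finding at Visit 2 is therefore dated Day 1.

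4. **Both rules applied**, with an illustrative first dose at 08:00:

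| Onset on Day 1 | SAP 10.2 calendar rule | Start at first dose | Before first dose? |
|---|---|---|---|
| 07:15 | TEAE | pre-treatment | yes |
| 08:30 | TEAE | TEAE | no |
| no time recorded | TEAE | TEAE by convention | unknown |

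   Only the first row changes.

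5. **Double entry.** Footnote a to Protocol 8.2.2 requires a pre-treatment event that changes intensity to be recorded as two events. If it starts before dosing on Day 1 and changes after dosing, both records lie inside the calendar window and both enter the event count of SAP 10.2.1 and 10.2.2. With a first-dose start, only the second does. The count of subjects with a TEAE would be the same either way in that case.

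6. **Size.** The plan's 19 per arm reproduces: 15 / (1 − 0.20) = 18.75, rounded up to 19, or 38 in total. One subject is 1/19 = 5.3%, above the 5% threshold for the frequent-TEAE table in SAP 10.2.2. How many events would fall in the interval cannot be derived from the documents.

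**The case against.** The best reply is that SAP 10.2 should be read whole. It repeats the protocol's definition, and the day ranges mainly serve to fix the end of the window. On that reading, an event before any IMP did not begin while IMP was being received. Protocol 8.1 gives no clock-time start either, so the SAP's statement that it does not deviate from the protocol proves little. This is fair, but it leaves a general sentence and a specific rule that give different answers for the same event.

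A second reply is that counting by date is a conservative convention, since onset time may be omitted from the log (Protocol 8.2.2). That is a good reason for untimed events. It is no reason to count an event whose recorded time precedes the dose.

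Several stronger readings are tempting, and the documents do not support them:

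- *Every pre-dose finding on Day 1 becomes a TEAE.* Most would not be adverse events at all, given the rule on pre-existing conditions.
- *All Day 1 pre-dose checks come after randomization.* Footnote e allows either order.
- *The nasal route is common.* It needs a new ulceration or perforation within about a week of screening. Protocol 3.5.6 also requires withdrawal when an exclusionary condition develops. A subject withdrawn before any dose is outside the safety set (SAP 6.4) and cannot enter these tables.
- *Using one observation as baseline and as a TEAE corrupts the shift or change tables.* The baseline value is still the correct pre-dose value, and no change score is wrong.
- *Pre-dose events will be tabulated as related.* The SAP default to related applies only when causality is unknown, and Protocol 8.2.2 requires the investigator to classify it.
- *The 5.3% measures this defect.* Any single event in an arm of 19 gives that figure.

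The rule is also the same in both arms and is applied to blinded records, so it adds noise and not a built-in direction.

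**Conclusion.** The point holds as a minor inconsistency. Under the working rule in SAP 10.2, an adverse event with onset on Day 1 before the first dose is a TEAE, whereas the protocol's footnote calls it pre-treatment. SAP medication coding and safety baselines are likewise cut at the first administration or first dose, so the TEAE window is the odd one out.

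Few events are likely to be affected. That is a judgement from the short interval and the narrow routes into it, not a figure in the documents. The conclusion assumes that the calendar rule is coded as written. If the programmer follows the general sentence instead, the problem does not arise, but the SAP does not say which prevails. Efficacy results are unaffected.

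**What to change.** In SAP 10.2:

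- Start the Treatment Period at the date and time of the first IMP administration, for completers and for subjects who discontinue.
- List adverse events with a recorded onset time before that dose as pre-treatment, and leave them out of the TEAE tables.
- Count Day 1 adverse events with no onset time as TEAEs.
- Leave the end of the window as it is.

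The SAP should not infer timing from the schedule, for example by treating an untimed event as pre-dose because it came from a pre-dose assessment. The log items in Protocol 8.2.2 do not include the source assessment, and nasal examinations precede all three Day 1 doses, so such a rule could remove events that followed the first dose.

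The cost is a short SAP edit and one condition in the derivation, best made before unblinding. Onset time is already a log item. The time of the Visit 2 morning dose is needed in any case, because all three sampling schedules in Protocol 7.2.6 include samples timed after it. The team should confirm that it is held in the database. The remaining downside is that an untimed Day 1 event that was in fact pre-dose is still counted.

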### **7.2.2 Physical Examination**

A complete physical examination including general appearance, head, eyes, ears, nose, and throat (HEENT), neck, cardiovascular, thorax/lungs, breasts, abdomen, genitourinary, musculoskeletal, lymph nodes, skin, neurological and mental status examination, will be performed by the Investigator or a delegated Sub-Investigator (a medically licensed, qualified trial team member) at Visits 1 and 4.

At screening, each category will be evaluated as normal, abnormal not clinically significant or abnormal clinically significant. Abnormal clinically significant findings at screening must be reported on the Medical History Log.

At end-of-trial, potential changes from screening to end-of-trial will be evaluated for each category. In case of changes, these will be evaluated as normal, abnormal not clinically significant or abnormal clinically significant. Abnormal clinically significant changes from screening to end-of trial must be recorded as AEs.

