#### 10.2.1 Overview of Treatment-Emergent Adverse Events

A TEAE overview summary table will be prepared including the number of subjects reporting a TEAE, the percentage of subjects (%) with a TEAE, and the number of events (E) reported, for the following categories:

- Treatment-emergent adverse events
- Treatment-emergent adverse events leading to Deaths
- Treatment-emergent adverse events by intensity
- Serious treatment-emergent adverse events

- Treatment-emergent adverse events leading to withdrawal
- Adverse drug reactions

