### **10.2.2 Incidence of Adverse Events**

TEAEs will be summarized in a table by treatment, system organ class (SOC) and preferred term (PT). The table will display the total number of subjects reporting a TEAE, the percentage of subjects (%) with a TEAE, and/or the number of events (E) reported. TEAEs will be presented by SOC sorted alphabetically and PT sorted in decreasing frequency of occurrence.

Summary tables will be prepared for:

- All TEAEs
- TEAEs with an incidence [ $\geq 5\%$ ] of subjects in any treatment group
- TEAEs by causality (related/unrelated)
- TEAEs by intensity

Supporting data listings will be provided for:

- All adverse events
- Serious adverse events
- Adverse events leading to withdrawal.

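### After early stopping, a new laboratory or examination AE found two or more days after the last dose enters no clearly specified AE table, yet the same Day 15 finding in a completer does

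*Combined protocol and SAP*

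**What the plan says.** SAP 10.2 defines a TEAE as "any adverse event that begins during the treatment period or worsening of a pre-existing medical condition". The first limb depends on the Treatment Period; the second, as printed, has no time limit. For completers the Treatment Period runs from Day 1 to Day 15. For the others: "For subjects who discontinued IMP, the Treatment Period is Day 1 to the dose date + 1".

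The AE tables are built on TEAEs. SAP 10.2.1 says: "A TEAE overview summary table will be prepared including the number of subjects reporting a TEAE". The four incidence tables in SAP 10.2.2 (all, at least 5%, by causality, by intensity) are TEAE tables too. The listings of all AEs, SAEs and AEs leading to withdrawal have no such limit. Protocol 9.8.2 follows the same pattern: all AEs listed, TEAE incidence tabulated.

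Three protocol rules turn findings into dated AEs:
- Protocol 8.2.2, for an AE that is a clinically significant laboratory or examination result: "the onset date is the date the sample was taken or the examination was performed".
- Protocol 7.2.3, on nasal examination: "After randomization, grading of 3 or 4 will be documented as an adverse event".
- Protocol 7.2.2, on physical examination: "Abnormal clinically significant changes from screening to end-of trial must be recorded as AEs".

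After Day 2, Table 1 of the protocol schedules safety laboratory tests, nasal examination and physical examination only in the column headed "End of Treatment Visit / Early termination visit". Protocol 3.5.6 asks withdrawing subjects who have been dosed to undergo the Visit 4 procedures first, but gives no number of days from the last dose.

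**The concern.** For a subject who stops at home, the early-termination visit is the only scheduled occasion after Day 2 on which a laboratory, nasal or physical examination abnormality can be found. If the visit is later than the day after the last dose, a new finding is dated outside the window. Whether it is counted then depends on travel time rather than on exposure or on the finding itself. A completer with the same finding on Day 15 is counted.

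Safety and tolerability is a stated objective. If stopping differs between arms, the by-arm AE counts are built on different rules for the subjects in whom tolerability matters most. SAP 10.3.3 has the same cut-off: its table of markedly abnormal laboratory values is confined to the treatment period. The vital-sign table in SAP 10.4.1.2 is confined to treatment-emergent values, a term the SAP defines for events but not for measurements.

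**Working it through.** **Inputs.** Window rule: SAP 10.2. Onset rule: Protocol 8.2.2. Visit schedule: Protocol Table 1. Planned doses, 42: SAP 8.1.2. At least 19 randomized per arm: SAP 3.2. The word missing before the dose date is taken to be last.

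**1. Reproduce the plan's own figure.** Window end = last dose day L + 1. For a completer, 14 + 1 = Day 15, as SAP 10.2 states. This supports reading the rule for early stoppers as last dose date + 1.

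**2. Apply the rule to early stoppers.** Onset on day L + 2 or later is outside. A Day 15 assessment lies 15 − (L + 1) = 14 − L days outside:

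| Last dose day L | Window ends | Day 15 finding |
|---|---|---|
| 1 | Day 2 | 13 days outside |
| 7 | Day 8 | 7 days outside |
| 11 | Day 12 | 3 days outside |
| 13 | Day 14 | 1 day outside |
| 14 (completer) | Day 15 | inside |

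**3. Can the assessment be that late?** The documents set no interval. Off-site doses are 42 − 2 × 3 = 36, and 36/42 = 86%, so most stopping would occur at home. This share does not measure how late visits are. Protocol 3.5.1 expects many subjects to live far from the site. SAP 9.1 makes conditional provision, for HPWSQ-R only, for Day 15 assessments in subjects who stopped before Day 12. A late visit is therefore plausible, but its frequency is unknown.

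**4. How much of the safety assessment is affected?** For a subject who stops after Day 2, the early-termination/Visit 4 assessment supplies 1 of 1 scheduled post-dose physical examinations and 1 of 2 scheduled post-dose safety laboratory draws (the other is on Day 2).

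**5. Where would a new finding outside the window be displayed?**
- AE tables: none of the 5 TEAE tables (1 overview + 4 incidence), subject to one ambiguity. The overview row for adverse drug reactions is not labelled treatment-emergent, and Protocol 8.1 gives that term no time limit, but the row sits in a table of subjects reporting a TEAE.
- Markedly abnormal laboratory table (SAP 10.3.3): excluded. The any-time flagged listing (SAP 10.3.4) includes it.
- Laboratory shift tables (SAP 10.3.2): can appear, because they use the worst post-baseline value.
- Nasal grade and shift tables (SAP 10.5.1): can appear.
- Physical examination: SAP 7.4 specifies listings only, although SAP 10.1 promises summary tables for all safety information. The table shells are a separate document (SAP 14) that was not available.

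**6. Size.** One subject is 1/19 = 5.3 percentage points, assuming 19 treated per arm. AE collection beyond the window, if the call is on Day 19, lasts 19 − (L + 1) = 18 − L days: 4 for a completer, 10 for L = 8, 15 for L = 3. The last two assume the call is still made after early stopping. For completers, the ±3-day allowance gives 1 to 7 days.

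**The case against.** The strongest reply is that this is a prespecified convention, not an error. The SAP allows one day for residual drug effect, applies the same rule to everyone, and tabulates TEAEs while listing all AEs, as the protocol planned. Nothing in the documents shows that one day is too short. That stands, and it is why the definition should not be changed.

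The affected case is also narrow. The subject must stop early, the assessment must fall two or more days later, and the finding must be new and itself a laboratory or examination result. Symptoms are dated to when they were first noted. In a trial of about 38 subjects, the listings can be read in full. These points also stand and limit the size.

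A reader might infer that safety findings in early stoppers are lost, or that the events which cause stopping go uncounted. The documents do not support this. Events that cause stopping would normally begin inside the window. Worsening of a pre-existing condition counts without a time limit. Every AE is listed, and laboratory values and nasal grades can reach tables of their own.

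The reply leaves one thing unanswered: the same new finding at the same Day 15 visit is counted in a completer and not in a subject who stopped. Shift and grade tables show values and grades, not AEs with causality, intensity and seriousness.

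**Conclusion.** The concern holds as a minor gap in tabulation. It is confined to new laboratory or examination AEs first detected two or more days after the last dose in subjects who stopped early, and to markedly abnormal laboratory values at that assessment. The number affected cannot be estimated from the documents and may be zero.

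The conclusion rests on reading the dose date as the last dose date, on the overview row for adverse drug reactions being limited to TEAEs (unclear), and on the separate shells adding no table of later AEs (unknown). It does not imply that the one-day window is wrong or that data are withheld.

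**What to change.** Leave the TEAE definition and TEAE tables as they are. Before unblinding, make these changes to the SAP:

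1. Add one by-arm table of AEs with onset after the Treatment Period through the Day 19±3 call, including those found at the early-termination/Visit 4 assessment. Show the number of subjects and the days observed per arm. Count each event once, here or in the TEAE tables.
2. Include the early-termination/Visit 4 assessment in the markedly abnormal tables for laboratory values (SAP 10.3.3) and vital signs (SAP 10.4.1.2), flagging values later than last dose date + 1.
3. As editorial clarifications, print the word last before dose date in SAP 10.2 and state whether the adverse drug reactions row is limited to TEAEs. A note in SAP 12 is optional.

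The cost is SAP text, one extra table and some programming. The data are already collected and the protocol does not change. The drawback is that off-drug observation time is unequal between subjects, and between arms if stopping differs. Keeping the table separate and showing days observed makes that visible.
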